#### 4.0 DEVICE DESCRIPTION/ DEVICE MODIFICATION DETAILS

[figure not shown]
The IDE study will include 3 device options for subjects with TAAA. As described below, subjects will be offered treatment with either a commercially manufactured custom device (CMD), the commercially manufactured standard device (t-Branch) or a physician modified endograft. All 3 devices work on the same principles and utilize similar component parts.

It is expected that most patients will be treated with a CMD device as this offers the optimal advantages of individual customization and commercial manufacturing. CMD will be the preferred device option and is expected to be used in a majority of cases. For some patients, the 6-8 week delay between stages is not feasible, either due to medical urgency (symptomatic aneurysm, large aneurysm size, or concerning aneurysm morphology (i.e. extremely saccular)) or due to logistical difficulty (patient's inability to travel to the University of Washington for repeated visits.) The University of Washington is the only medical center in the 5 state WWAMI region (Washington, Wyoming, Alaska, Montana, and Idaho) that currently offers endovascular treatment of TAAA. Patients have also been referred from Utah, Oregon and California. Some patients have to travel very long distances (at their own expense) and cannot afford to travel for multiple pre-operative visits. In this case, we may elect to use t-Branch or a physician modified device. As described below, the t-Branch device would be used for large and longer extent aneurysms that cannot be delayed for a CMD. Physician modified devices are preferred for aneurysms with a narrow peri-visceral aorta (i.e. dissection, or extent 1/4/5 aneurysms) and for extent 4 aneurysms that can be treated with a shorter length of aortic coverage than a t-Branch would require.

- 4.0.1 Physician modified fenestrated-branched thoracic endovascular grafts are delivered via catheters and sheaths to treat thoracoabdominal aortic aneurysms (TAAA). The technique is based on the Zenith® TX2® Endovascular Graft which is commercially available in the United States. The stent graft is designed to reline the diseased vasculature, providing an alternate endovascular blood conduit for isolating the aneurysm from the high pressure flow of blood, thereby reducing or eliminating the risk of rupture. The stent graft is a single piece tube graft configuration. The device is intended to be used as a modular device, with proximal seal achieved either by the physician modified Zenith® TX2® device itself or with one or more proximally deployed un-modified Zenith® TX2® devices. The distal seal is achieved with either the physician modified TX2® device, a more distally deployed un-modified TX2® device, or by using commercially available infra-renal aortic stent grafts, including the COOK Zenith® Flex® and Endologix AFX™ devices deployed into the iliac arteries.. The customized physician modified fenestrated-branched graft is deployed to reline

the peri-visceral aorta and ensure visceral branch perfusion (i.e. celiac, superior mesenteric, inferior mesenteric, renal and/or dominant spinal arteries) while excluding the thoracoabdominal aneurysm.

The physician modified device offers absolute customization within the anatomic inclusion/exclusion criteria. The device has been successfully narrowed down to 16 mm at the level of 2 renal fenestrations. Fenestration position can be adjusted to within 1mm in arc length. The disadvantage of this construct is that it uses fenestrated-branches, so it requires long branches when the aneurysm is large at the peri-visceral level. Furthermore, as the device is manufactured by the physician, there is not the same standardized manufacturing process used for the commercially manufactured device.

Figures 1

[figure not shown]

Figure 2

Figure 3

Figure 4

**4.0.2** The Cook CMD branched and/or fenestrated-branched endograft is comprised of similar modular components and works by the same principles as used in the physician modified construct. This system uses a Cook TX2 or Alpha device with cuffs and/or fenestrations that are created according to standardized manufacturing techniques. The cuffs and fenestrations are selected for each subject based on their unique anatomical constraints. The cuffs are discussed below. The fenestrations work in the same

manner as those created in the physician modified construct. As with the physician modified options, the proximal fixation is achieved with unmodified Cook TX2 or Alpha Thoracic endografts or with the branched/fenestrated device itself. The distal seal is achieved either with the distal segment of the branched/fenestrated component, a Cook TX2 or Alpha endograft deployed in the infra-renal aorta, or with the Cook Distal Bifurcated Endovascular Stent Graft (CDBG). The CDBG is a bifurcated stent graft identical to the Cook Zenith Flex graft except that it has no supra-renal fixation. The absence of supra-renal fixation allows the CDBG to be placed within the branched fenestrated graft without interference with the renal branches. The device is bifurcated and designed to be used in a modular device with Cook Spiral Z iliac extension limbs to seal into the iliac arteries. The CMD option includes all the design advantages of the physician modified device, with the additional benefits that down-going cuffs can be used instead of fenestrations in large aneurysm sacs and the reliability of standardized commercial manufacturing. The disadvantage of this option is that it requires 6-8 weeks for graft design, manufacture and importation.

**4.0.3** The Cook t-Branch construct is a specific design of the Cook CMD that is intended to treat a majority of patients with TAAA. It has downgoing cuffs positioned such that most patients with TAAA could be treated with this specific device. Again, proximal and distal fixation is achieved in the same manner as the Cook CMD. As this device can be pre-fabricated and kept available, it can be used for patients with eligible anatomy without having to wait for a CMD device to be manufactured. This device uses 4 downgoing cuffs. Therefore, it requires a minimum of 25 mm of aortic flow channel at the peri-visceral level to have enough working room to selectively catheterize the target vessels. The device length requires that the proximal seal/fixation zone for the device is 24-30 mm as measured 140 mm above the SMA position in a centerline measurement. The minimal length of aortic coverage is therefore at least 14cm above the SMA position and it extends down into both common iliac arteries.

#### **4.0.4** Summary of Advantages of each device option:

##### Advantages of the Cook Custom Modified Device

##### (CMD):

- Downgoing cuffs allow for greater degree of intra-operative adjustability compared to fenestrations and may provide improved stability in very large aortic flow channels by virtue of increased device to device overlap between the aortic and branch stents.
- Downgoing cuffs allow for earlier closure of femoral access to shorten pelvic/leg ischemic time in patients with hostile ilio-femoral access, as branches can be created from arm access after deployment of the aortic devices.
- Downgoing cuffs may facilitate branch stenting of very downgoing branch arteries.
- Downgoing cuffs and fenestrations can be combined to create the optimal device for each specific patient.
- Length of coverage of the aorta can be adjusted based on selection of cuffs or

fenestrations.

- Commercial manufacturing carries assurances of standardized manufacturing protocols, which are not possible in the physician modified option.

Advantages of the Cook t-Branch:

- The t-Branch uses down-going cuffs, so the same advantages apply as described above.
- As the device is pre-manufactured, it is readily available for patients with symptomatic or large aneurysms, or those that cannot delay treatment for 6-8 weeks for a CMD device to be manufactured.

Advantages of the Physician Modified Device:

- Device can be manufactured immediately, so this is preferred for symptomatic patients and those with very large aneurysms at risk of imminent rupture if the patient's anatomy is not amendable to the standardized t-Branch commercial device design.
- Physician modification can allow for very precise fenestration adjustment, including direct permanent diameter reduction of the Z-stents to refine alignment in small aortic flow channels, so it is preferable in some patient anatomies compared to the t-Branch device.
- The physician modified device option can be done with short aortic devices, potentially allowing for treatment with less aortic coverage in selected patient anatomies (e.g. focal peri-visceral pseudoaneurysms). Shorter length of coverage may reduce the risk of spinal cord injury.
- The physician modified device is designed to be implanted from femoral access. The avoidance of brachial access may reduce the risk of periprocedural stroke or neurovascular injury to the arm.

#### **4.0.4 HOW DEVICE SELECTION WILL OCCUR**

Patients enrolled in the B-TEVAR IDE study will meet the same inclusion/exclusion criteria. Once enrolled, patients will be recommended treatment with the CMD option unless one of the following criteria are met:

- 1) they have a symptomatic aneurysm
- 2) they have a very large aneurysm at risk of imminent rupture (fusiform aneurysm >7.5 cm, very irregular saccular aneurysm)
- 3) the patient is unable to afford the required repeated visits for study enrollment and then treatment that would be required by a 6-8 week delay
- 4) the patient prefers to be treated earlier than the 6-8 week delay

For those subjects who meet 1 or more of these 4 criteria, then they will be offered treatment with the t-Branch of physician modified options based on their anatomy. As described above, each option has advantages in different anatomic situations, and this will dictate which device is used. Aneurysms with large peri-visceral component and very

down-going target vessels would be better served with a t-Branch device. Aneurysms with narrow aortic flow channels at the visceral level or those that can be treated with shorter aortic coverage will be better served with a physician modified device. Subjects with small iliac artery access would be better treated with the Zenith cook Low Profile t-Branch or Custom Modified Device.

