## 2.0 BACKGROUND AND RATIONALE

13,000 Americans die each year from rupture of an aneurysm in the aorta, which is the ninth leading cause of death in men over age 55. Aortic aneurysms are four times more common in men than in women and usually occur in those over age 50. Approximately one percent of men between the ages of 55 and 64 will have a significant aneurysm, and the likelihood increases to about four to six percent of those men over the age of 75.

Aortic aneurysms that involve the arteries to the intestines and kidneys are called thoraco-abdominal aortic aneurysms (TAAA) and are classified according to the Crawford classification system as modified by Safi. The risk factors for degenerative TAAA include tobacco use, hypertension, hyperlipidemia, male sex, and family history. Approximately 80% of TAAA are due to aortic atherosclerotic degeneration. An additional 20% develop TAAA as a consequence of aortic dissection with dilation of the false lumen.

Elective treatment of TAAA is done to prevent rupture. Without operation, about 25% of patients not deemed fit for surgery die within 1 year due to rupture. Traditional surgical therapy

involves an extensive incision extending from the chest to the abdomen. Cardiopulmonary bypass is often required. The operation carries significant risk of morbidity and mortality. Large population based studies have found a 20% peri-operative mortality which rises to 30% at 1 year.

Endovascular therapy has been developed to treat aneurysms involving the thoracic and abdominal aorta. Endovascular stent grafts have significantly reduced the peri-operative risk of surgery. Given the morbidity associated with open operation for TAAA, there is great optimism that endovascular therapy may significantly reduce the peri-operative risk of TAAA repair as well. Because TAAA involve the vital visceral blood vessels to the intestines and kidneys, an endovascular treatment must preserve flow to these branches while excluding flow from the aneurysm. Currently, there are no commercial endografts available to treat aneurysms involving the peri-visceral aorta.

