### **2.1.4 Branched Endovascular Stent Graft Repair**

There are several studies describing endovascular technologies for preserving vital aortic branch vessels during the course of endovascular repair of TAAA. Three treatment options have been reported. The first two utilize commercially manufactured stent grafts by Cook Medical. This includes a custom modified device (CMD) and the t-Branch standardized device. These devices are not FDA approved and are only in use under Physician Sponsored IDE studies in the USA. They are approved for use in Europe and are currently available for use there. The alternative option is physician modification of a commercial endograft to create reinforced fenestrations. This study currently utilizes physician modified endografts, and the purpose of this supplement is to add the commercial manufactured grafts as options for subjects in this study.

The largest in-human experience currently available for endovascular treatment of TAAA comes from two centers in the USA that have used a combination of a CMD and the standardized t-Branch option manufactured by Cook Medical. The CMD devices are customized to the patient's anatomy and require 6-12 weeks for manufacture in Australia prior to implantation. The t-Branch option is a single design that utilizes 4 down-going cuffs to allow for intra-operative flexibility in treating variable branch anatomy. Initial results from these centers have been very encouraging, and important lessons have been learned.

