Patients will be enrolled in B-TEVAR study with a plan for 2 different pathways to treatment, either in single sitting or in a staged approach. For those patients in whom a staged approach is planned or considered, consent will be obtained and the patient enrolled prior to undergoing the TEVAR 1st stage of the procedure. These patients will be tracked with a separate follow up case report form at 1 and 12 months and annually to 5 years or until they undergo the second stage with a branched device, at which time their outcomes will be followed according to the routine case report forms. Some patients who undergo the 1st stage will not go on to have the second stage done with a branched graft. This could be due to the determination that they can indeed tolerate open repair, or due to a complex recovery after the 1st stage TEVAR. Such patients will be followed up to 5 years after enrollment. All patients who are enrolled will be followed and reported on. Patients who undergo the first stage, but not the second stage, will be reported as a sub-group of patients in the annual report.

All patients who undergo the first stage TEVAR will be treated with the same TX2 device that is in the B-TEVAR protocol. The specific peri-visceral device used for the second stage could be any one of the 5 device options, CMD, t-Branch, LP CMD or t-Branch or physician modified.

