### Step 3: Study Enrollment

Subjects who meet all 3 criteria listed in Step 2, as determined by both the PI and the CT ICU physician, will be provided the opportunity to participate in the study. Signed written consent will be obtained and subject will enroll in the study.

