#### 6.5 Post-Treatment follow-up period

The following assessments and tests will be performed at the following intervals:

Time period post-treatment	Acceptable visit timeframe allowance
1 Month (30 days)	± 14 days
6 Months (180 days)	± 30 days*
12 Months (365 days)	± 45 days
Annually from 2 to 5 years	± 60 days

\*This will not be done for those undergoing TEVAR only

- Physical exam
- Laboratory testing to assess renal function and, if needed, to measure CBC
- Contrast Enhanced Spiral CT of the Chest/Abdomen/Pelvis OR for patients unable to receive IV contrast, a non-contrast thin cut CT scan of the Chest/Abdomen/Pelvis will be performed as well as a duplex of the abdominal aorta to assess the branch patency, velocity and to look for the presence of endoleak and aneurysm sac size (\* for subjects undergoing the TEVAR first stage, no aortic duplex will be performed)
- Device/aneurysm assessment based on imaging (endoleak, migration, integrity, patency, TAAA dimensions)
- Concomitant medications - anticoagulants, anti-platelets, antibiotics, statins, Beta-blockers and ACE inhibitors/ARBs
- Adverse events
- Other relevant data as indicated on the CRF including optional wound assessment.

The above assessments are recorded in the appropriate **Follow-up CRF**.

All subjects who have undergone the B-TEVAR device implantation, whether in a single or multiple stage will be followed with the B-TEVAR Follow-up CRF and will be analyzed as a

single group as well as by subgroup of device type. The date of implantation of the modified device will serve as the start time for follow up. Subjects who do not undergo the second stage of a planned staged repair will be analyzed separately and evaluated for survival and cause of death. With the exception of data points specific to the branched graft (i.e. branch complications, migration, etc.) the same clinical data points will be recorded for patients who only undergo the first stage of a staged repair, including medical demographics, aneurysm size and extent, and major adverse events. Additional information for the TEVAR alone will include a rationale as to why the second stage was not completed. For the two staged approach, the time interval between Stage 1 and Stage 2 will be recorded. Complete data will be reported for each group. Outcomes based on subgroup analysis of those who had single repair, staged repair and those who only had the initial stage and did not complete the second stage will also be reported.

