#### 9.1.2 Effectiveness

The primary effectiveness endpoint is the proportion of treatment group subjects that achieve treatment success with the B- TEVAR procedure, whether via the staged approach or done as a single procedure . Treatment success is a composite endpoint assessed at 12 months after the B-TEVAR procedure is performed that requires all of the following criteria to be met in order for a patient to be considered a treatment success:

- Technical Success, defined as successful delivery and deployment of the endovascular graft with preservation of unimpeded flow to those branch vessels intended to be preserved.
- Freedom from Type I & III endoleak. Type I and III endoleaks will be assessed by the investigator using Spiral CT images.
- Freedom from stent graft migration. Migration of the aortic stent graft is defined as evidence of proximal or distal movement of the stent graft >10 mm relative to fixed anatomic landmarks. Migration of a branch is defined as movement of the stent in relation to fixed anatomic location that results in a Type I or III endoleak. Spiral CT images will be used by the investigator to determine migration from the one month (baseline) CT image.
- Freedom from TAAA enlargement. Sac enlargement is an increase in aneurysm diameter (>5 mm) from the one month (baseline) post-operative measurement will be considered TAAA enlargement, as determined by the investigator.
- Freedom from TAAA rupture
- Freedom from conversion to open repair

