## APPENDIX IV: SCHEDULE OF ACTIVITIES

Procedure	Baseline	Treatment	Discharge	1 Month Follow-Up	6 Month Follow-Up 	12 Month Follow-Up	Annual Follow-Up
Medical/Surgical History	X 						
Physical Exam	X 		X	X	X	X	X
Spiral Contrast Enhanced CT	X 			X 	X 	X 	X 
Laboratory Assessment (creatinine, PT, PTT, INR, CBC)	X 		X 	X 	X 	X 	X 
Adverse Event Assessment		X	X	X	X	X	X
Concomitant Medication Assessment (anticoagulants, antiplatelets, antibiotics, ACE inhibitors, Beta blockers and statins only)	X		X	X	X	X	X
Device/aneurysm assessment based on imaging (endoleak, migration, integrity, patency)				X	X	X	X

 CBC, PT, PTT and INR are optional after Baseline.

 Baseline med/surgical history, physician exam performed no more than 3 months prior to the implant/surgical procedure.

 Laboratory assessments performed no more than 3 months prior to surgical/implant procedure

 Serum pregnancy HCG test for females of childbearing potential performed no more than one week prior to surgical/implant procedure

 Baseline contrast enhanced CT must be obtained within 4 months of anticipated treatment date.

 If subject not able to tolerate contrast enhanced CT, a non contrast CT and visceral branch duplex ultrasound can be performed

 Subjects who undergo TEVAR only will not have the 6 month visit

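### Subjects are enrolled before the custom-graft (CMD) manufacturing wait, but follow-up, scheduled event collection and reporting groups start at the procedure, so CMD results are conditional on reaching implant

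*Protocol*

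**What the plan says.** **Order of events.** Section 6.1 puts consent and enrolment at Step 3, ahead of the procedure at Step 4: "Signed written consent will be obtained and subject will enroll in the study". Section 4.0.4 (How device selection will occur) then makes CMD the default: "Once enrolled, patients will be recommended treatment with the CMD option unless one of the following criteria are met". Section 4.0 expects CMD in a majority of cases.

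**Length of the wait.** Sections 4.0.2 and 4.0.4 give 6-8 weeks for a CMD. Section 2.1.4 says such devices "require 6-12 weeks for manufacture in Australia prior to implantation".

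**Clock and analysis groups.** Section 6.5 states: "The date of implantation of the modified device will serve as the start time for follow up". It analyses everyone who received the B-TEVAR implant, as one group and by device type, and handles separately those who had only the first stage of a staged repair. The subgroups it names are single repair, staged repair and first stage only. Section 9.0 requires endpoints pooled and by graft construct.

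**Event collection.** In Appendix IV the row "Adverse Event Assessment" is blank at Baseline and first marked at Treatment. Step 4 of section 6.1 provides follow-up forms only after B-TEVAR or after first-stage TEVAR.

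**Denominator.** Section 5.0 enrols 60 patients and section 5.2.1 calls these 60 the Treatment Group. Section 9.1.2 builds on that: "The primary effectiveness endpoint is the proportion of treatment group subjects that achieve treatment success". Section 2.1.4 promises: "All patients who are enrolled will be followed and reported on".

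**The concern.** The procedure exists to prevent rupture, and the protocol's background describes untreated disease as dangerous: "about 25% of patients not deemed fit for surgery die within 1 year due to rupture". A single-stage subject assigned to CMD carries that untreated risk for weeks after joining the study. A bad outcome in that window falls outside the follow-up clock, the event schedule and every group named in section 6.5.

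Two things are at stake. First, the CMD figures describe only those who stayed alive, unruptured and fit enough to reach implant. The physician-modified and t-Branch options have little or no manufacturing wait, so the same selection barely touches them, yet section 9.0 sets the three constructs side by side. Second, the document gives two answers to who is counted: 60 enrolled subjects under 5.0, 5.2.1 and 9.1.2, but implanted subjects under 6.5. The two differ by exactly the subjects in question.

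**Working it through.** **Step 1. Trace one subject.** Take a single-stage subject enrolled for a CMD who ruptures in week 5.
- Time origin: none, because section 6.5 starts at implantation.
- Primary safety (9.1.1): timed at 30 days after the branched repair, so no window opens.
- Primary effectiveness (9.1.2): assessed 12 months after B-TEVAR, so no assessment date exists, although the subject is one of the Treatment Group.
- Secondary endpoints: the Protocol Summary times mortality and rupture from implantation.
- Scheduled event collection (Appendix IV): begins at Treatment.
- Reporting group (6.5): none of the three fits. The subject is not a screen failure either, since section 6.2 reserves that term for patients who do not qualify.
- Risk section (10.0): names interval rupture only between stages.

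Section 2.1.4 nonetheless promises that this subject is followed and reported.

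**Step 2. Illustrate the size.** The protocol states no figure for events during the wait, so there is none to reproduce. Inputs:
- One-year rupture death without operation: p = 25% (section 2.0). Section 2.1.1 is consistent with it: 55% dead by a median of 12 months, half from rupture, gives 0.55 × 0.5 = 27.5%.
- A lower case of p = 12.5%, half the annual risk. This is an assumption: symptomatic and very large aneurysms are steered away from CMD, and enrolled subjects need a life expectancy above one year.
- Wait w = 6 or 8 weeks (4.0.2, 4.0.4).
- CMD subjects: 31-45 of 60. A majority means at least 31; 45 is an assumption.
- Constant hazard (assumption), with 52.18 weeks in a year.

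Risk over the wait = 1 − (1 − p)^(w/52.18).

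| Annual risk | 6 weeks | 8 weeks |
|---|---|---|
| 25% | 1 − 0.75^(6/52.18) = 3.25% | 1 − 0.75^(8/52.18) = 4.31% |
| 12.5% | 1 − 0.875^(6/52.18) = 1.52% | 1 − 0.875^(8/52.18) = 2.03% |

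**Step 3. Convert to subjects.**
- All CMD subjects single-stage: lowest 31 × 0.0152 = 0.47; highest 45 × 0.0431 = 1.94. About 0.5-1.9.
- Half of them single-stage (assumption; the share is not given): 15.5 × 0.0152 = 0.24 to 22.5 × 0.0431 = 0.97. About 0.2-1.0.

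**Step 4. What one subject is worth.** In a CMD group of 31-45, one uncounted subject is 1/45 = 2.2% to 1/31 = 3.2% of the group.

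**The case against.** The strongest reply is that the protocol already has places to put such an event. The Adverse Event form (8.9, 8.10) does not require an implant, withdrawals go on the Study Completion/Exit form (5.3), and section 9.2.1 has the clinical events committee adjudicate every death in the study. This stands. A reader might infer that a death during the wait could not be recorded at all, and the protocol does not support that. What is missing is scheduled collection, a time origin and a group in which to report it.

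A second reply is that section 9.1.2, read literally, keeps a never-implanted subject in the denominator as a failure of technical success. That reading is open, so certain exclusion from the primary effectiveness endpoint is not established. But it contradicts section 6.5, and the by-device analysis there is plainly of implanted subjects. An analysis plan, if one exists, could settle the denominator; it could not recover events that were never systematically collected.

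Third, a rate conditional on implant is a legitimate quantity in a non-randomised feasibility study. Section 9.0 asks for separate reporting, not a test between devices, and any comparison is already confounded because urgent cases go to other devices. This also stands, and is why enrolment-based figures belong beside the existing endpoints and should not replace them. Nor is this immortal-time bias: no waiting time is credited to the treated group. It is selection on reaching implant.

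Fourth, section 6.1 discusses device choice within Step 1, so the choice may be made before enrolment. Even so, section 4.0.4 describes enrolment followed by treatment after the delay, so the wait comes after enrolment either way.

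Last, larger numbers are tempting and should be resisted. The 55% death figure is all-cause, at a median follow-up in untreated patients, and does not carry over to this screened cohort. The 12-week figure appears only in background text. Some CMD subjects will be staged, and their wait may fall after stage 1, where TEVAR forms apply. The documents do not support a claim that the uncounted loss equals 30-day mortality in size.

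**Conclusion.** The point holds as a contradiction and a gap in the reporting rules. Section 6.5 and Appendix IV start at the procedure, whereas 2.1.4, 5.0, 5.2.1 and 9.1.2 commit the study to all enrolled subjects. The by-device CMD results are conditional on survival and fitness to implant, and the omission favours CMD.

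The size is modest and uncertain: about 0.5-1.9 subjects if all CMD subjects are single-stage and about 0.2-1.0 if half are. This rests on a constant hazard, an annual rupture-death risk of 12.5-25%, a 6-8 week wait and 31-45 CMD subjects. The 25% comes from patients unfit for surgery, so the upper end is probably too high for these subjects. The figures cover rupture death only and leave out subjects who become unfit. With 60 subjects in all, even one uncounted case would matter to a by-device rate, so the text should be corrected.

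**What to change.** 1. Reconcile section 6.5 with sections 2.1.4, 5.2.1 and 9.1.2 by adding a reporting group *enrolled, no aortic stage performed*, and say how these subjects enter the effectiveness denominator.
2. Record death, rupture and the reason for non-treatment from the date of enrolment, using the existing Adverse Event and Exit forms, and mark the enrolment-to-treatment period in the adverse event row of Appendix IV.
3. Record the device intended at enrolment.
4. Report mortality and rupture from enrolment by intended device, beside the implant-based endpoints, with the numbers enrolled and implanted for each.
5. Reconcile the 6-8 and 6-12 week statements of the manufacturing time.

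The cost is protocol wording and one form field, with no added patient or visit and no change to treatment. The downside for the sponsor is a slightly less favourable CMD figure.
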